5.3.3 Global Attainment Scale by Investigator/Therapist

Each of the 2 goals for each patient at each visit will be analyzed by an ANCOVA model with age group, principal muscle group, treatment group, study center and previous botulinum toxin exposure as factors and baseline MAS-B as a covariate to assess treatment differences. The frequency distribution of raw scores for each goal will be summarized by treatment group. Additionally, the percentages of responders who scored 0 or higher (meet or exceed expectation) and the responders who scored -1 or high (slight improvement but not meet expectation) on each functional goal will also be summarized and responder status will be analyzed by logistic regression with factors of age group, principal muscle group, treatment group, study center and previous botulinum toxin exposure, if applicable.

5.3.4

Modified Tardieu Scale of the Principal Muscle Groups

The change from baseline of the angle difference, R2-R1, and the individual R1 and R2 respective changes from baseline will be derived at each post-treatment visit and summarized by treatment group. An ANCOVA model with age group, principal muscle group, treatment group, study center and previous botulinum toxin exposure as factors and baseline MTS as a covariate will be performed to assess treatment differences. The raw scores of R2-R1, R2 and R1 will also be summarized and analyzed using similar methods.

5.5 Subgroup Analyses for Efficacy Variables

Subgroup analyses by the stratification factors of age (≤ 6 years and > 6 years), principal muscle group (elbow and wrist), and baseline MAS-B score (2 and > 2) and previous exposure to botulinum toxin will be performed for primary efficacy variable(s). The “None” subgroup for

previous exposure to botulinum toxin is defined as the patients who never received botulinum toxin in the past.

6 Safety Analyses

Safety variables including the incidence of adverse events, the incidence of suicide-related events using the C-SSRS (for patients \geq 6 years of age at day 1), lab tests values and their changes from baseline, as well as vital signs and their change from baseline, will be summarized by treatment group using the safety population.

6.1 Exposure to Study Treatments

Patient exposure to the study medication will be characterized by total dose in U, and dose in U/kg body weight.

Duration of follow up is defined as the number of days from the first injection to exit; if the date of exit is missing, the date of the last visit will be used. Data will be summarized with descriptive statistics for each treatment group.

In addition, the total dose in U and dose in U/kg body weight will be summarized by individual muscle, by each muscle group as well as for all muscles combined.

6.2 Treatment Emergent Adverse Events

Adverse events are collected both for the screening/baseline period prior to treatment (which are referred to as pre-treatment adverse events as cited in Section 4.6) and for the follow-up period after treatment is initiated.

A treatment-emergent adverse event (TEAE) is a post-baseline adverse event with onset after the initiation of study treatment or an adverse event with onset prior to study treatment that worsened in severity or became serious after the initiation of study treatment. The number and percentage of patients reporting each event will be summarized and presented for all events and tabulated by treatment groups (6 U/kg, 3 U/kg, and placebo) and overall as follows:

- i. By primary SOC and preferred term. At each level of summarization (overall, primary SOC, and preferred term) a patient will be counted once if he/she reports 1 or more experiences at that level.

- ii. By primary SOC, preferred term and severity. For a given adverse event of a patient, if more than 1 severity grade was reported, the worst severity grade will be included in the tabulation.

All treatment-related TEAEs (study drug-related and injection procedure-related TEAE) will be presented by primary SOC and preferred term. A listing of adverse events leading to discontinuation will also be provided.

The number and percentage of patients with any of the preferred terms will be summarized for each primary SOC and preferred term. All patients will be counted only once for each preferred term when multiple occurrences of the same preferred term are reported.

In addition, individual patient data listings (including adverse event listings that include the investigator verbatim terms and MedDRA lower level terms) will be provided.

Furthermore, the assessment of possible distant spread of toxin will be performed using the list of 39 MedDRA preferred terms (version 19.0 or its updated version as appropriate during the time of data analysis).

MedDRA Preferred Terms Evaluated for Possible Distant Spread of Toxin

Cardiac Disorders

Bradycardia

Eye Disorders

Accommodation disorder
Diplopia
Extraocular muscles paresis
Eyelid function disorder
Eyelid ptosis
Pupillary reflex impaired
Vision blurred

Gastrointestinal Disorders

Constipation
Dry mouth
Dysphagia
Ileus paralytic

Infections and Infestations

Botulism

Musculoskeletal and Connective Tissue Disorders

Muscular weakness

Nervous System Disorders

Bulbar palsy
Cranial nerve palsies multiple
Cranial nerve paralysis
Dysarthria
Facial paralysis
Facial paresis
Hyporeflexia
Hypotonia
Paralysis

Paresis cranial nerve
Peripheral nerve palsy
Peripheral paralysis
Speech disorder
Vocal cord paralysis
Vocal cord paresis

Renal and Urinary Disorders

Urinary retention

Respiratory, Thoracic and Mediastinal Disorders

Aspiration
Diaphragmatic paralysis
Dysphonia
Dyspnoea
Pneumonia aspiration
Respiratory arrest
Respiratory depression
Respiratory failure

Reproductive System and Breast Disorders

Pelvic floor muscle weakness

6.3 Serious Adverse Events

The number and percent of patients with serious TEAEs will be tabulated by treatment groups (6 U/kg, 3 U/kg, and placebo) and overall for all serious adverse events regardless of relation to treatment by primary SOC and preferred term.

6.4 Clinical Laboratory Evaluations

Hematology and non-fasting clinical chemistry assays will be obtained at screening and exit as specified below.

Hematology	hemoglobin	hematocrit	red blood cells
	white blood cells	neutrophils	bands
	lymphocytes	monocytes	basophils
	eosinophils	platelets	
Electrolytes	sodium	potassium	bicarbonate
	chloride	phosphorus	calcium
Chemistry	glucose	creatinine	urea nitrogen
	total bilirubin	alkaline phosphatase (total plus bone and liver fractions)	aspartate aminotransferase (serum glutamic oxalacetic transaminase)
	alanine aminotransferase (serum glutamic pyruvic transaminase)	albumin	
Other	hemoglobin A1c	25 hydroxyl vitamin D	Parathyroid hormone if alkaline phosphatase bone fraction is abnormal

These values at each visit and the change from baseline will be summarized by the treatment group by visits using descriptive statistics. All laboratory values will be listed. Laboratory values at each visit will also be categorized as low, normal, and high according to the respective reference normal ranges.

6.5 Vital Signs

Vital signs are assessed at screening, day 1, and exit. Blood pressure (diastolic and systolic measured in mmHg), pulse rate (beats/minute), respiratory rate (breaths/minute), and body temperature (°C), weight (kg) will be summarized by treatment group for each visit and change from baseline to exit visit will also be summarized by treatment group.

6.6 Columbia-Suicide Severity Rating Scale

Suicidality for age over 6 years will be assessed using the Columbia-Suicide Severity Rating Scale (C-SSRS), conducted at every assessment visit. Suicide-related events corresponding to the C-SSRS questions will be classified into the following 11 categories:

- Self-injurious behavior, no suicidal intent
- Suicidal ideation
 1. Wish to be dead
 2. Active: Nonspecific (no method, intent, or plan)
 3. Active: Method, but no intent or plan
 4. Active: Method and intent but no plan
 5. Active: Method, intent and plan
- Suicidal behavior
 1. Preparatory acts or behaviors
 2. Aborted attempt
 3. Interrupted attempt
 4. Suicide attempt
 5. Completed suicide

The number and percentage of patients with the above suicide-related events during treatment will be presented by treatment group. If a patient has more than one suicide-related event during an interval, the most severe event in increasing order listed above will be used.

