12.1.18 Columbia-Suicide Severity Rating Scale (C-SSRS)

The C-SSRS ([Posner et al, 2011](#)) is a semistructured interview designed to assess the severity and intensity of suicidal ideation, suicidal behavior, and non-suicidal self-injurious behavior over a specified time period (eg, prior year, since last visit). The measurement of suicidal ideation is based on 5 “yes” or “no” questions (plus a description if answered “yes”) arranged in order of increasing severity. If the patient answers “yes” to either question 1 or 2, the intensity of ideation will then be assessed in 5 additional questions relating to the frequency, duration, controllability, deterrents, and reasons for the most severe ideation. Suicidal behavior is then assessed by asking further questions to categorize the behaviors into actual, aborted, and interrupted attempts; preparatory behavior; and non-suicidal self-injurious behavior. The interview is used in full only if the initial questions are positive; this assessment is completed at all scheduled clinic visits at which other clinical assessments are to be carried out.

If any item(s) on the C-SSRS are answered with “yes”, a physician investigator must review patient’s responses in order to:

- a. at screening and baseline determine patient’s study eligibility and potential need for referral to a mental health professional, and
- b. during the study evaluate patient’s need for appropriate medical management such as referral to a mental health professional

A significant risk of suicide is defined as a “yes” in answer to: a) questions 4 or 5 on the suicidal ideation section; or b) any questions on any item in the suicidal behavior section.

This must be reported as a serious adverse event and followed up accordingly (see Sections 9.1.2 and 9.3 of the study protocol). Additionally, if a patient responds “yes” to any of the suicidal ideation questions 1 to 3, the investigator should apply clinical judgment to determine the need for reporting as an adverse event or serious adverse event and the need for any referral.

The C-SSRS is available in several versions designed for use in clinical trials. Appropriate versions of the scale will be used in this trial.

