2.2 Treatment Visits

All days are referenced to day 1. Day 1 is the randomization/treatment day. In the cases where randomization and treatment happened on different days, the day of treatment will be used as day 1. Visits according to the windows below will be determined for each variable analyzed unless noted otherwise in the following sections. If there are values from multiple visits in a given window, the value collected from the visit closest to the target day will be used to represent the window. If 2 visits with values fall within the same window and are equidistant from the target day, the value from the first of the 2 visits chronologically will be used to represent the window. For clinical laboratory variables, the last non-missing observation for that visit window

will be used. This rule will be applied separately for each variable for non-missing data only. (The exception is because re-runs of laboratory variables may only involve one or a few variables and would thus include missing data for many variables).

Visit	Target Day of the Visit	Visit Window (Day*)
Screening	-28	\leq Day -1
Day 1 (Randomization/Treatment)	1	Day 1
Week 2	15	Day 2 to Day 22
Week 4	29	Day 23 to Day 36
Week 6	43	Day 37 to Day 50
Week 8	57	Day 51 to Day 71
Week 12	85	\geq Day 72

* All days are referenced to day 1. For post-treatment visits, study day = visit date – day 1 date+1 while for pre-treatment visits, study day = visit date - day 1 date.

The visit windows will be used for by-visit analyses in both modified intent-to-treat (mITT) and safety population analyses.

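### SAP 6.6 ranks non-suicidal self-injury lowest of 11 C-SSRS categories, so its row omits any patient who reports another item in the same interval

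*SAP*

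**What the plan says.** SAP 6.6 lists 11 categories in this order: "Self-injurious behavior, no suicidal intent", then five ideation items starting with the wish to be dead, then five behavior items ending with completed suicide. It says: "The number and percentage of patients with the above suicide-related events during treatment will be presented by treatment group". For a patient with "more than one suicide-related event during an interval, the most severe event in increasing order listed above will be used".

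The SAP does not define the interval for this rule. Two readings are available:

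- The preceding sentence speaks of the treatment period as a whole.
- The scale is "conducted at every assessment visit", and SAP 2.2 states: "The visit windows will be used for by-visit analyses in both modified intent-to-treat (mITT) and safety population analyses". That points to visit windows, although SAP 2.2 does not mention the C-SSRS.

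Protocol 12.1.18 describes the scale as assessing the "severity and intensity of suicidal ideation, suicidal behavior, and non-suicidal self-injurious behavior over a specified time period". Later in the same section, non-suicidal self-injury appears among the behaviors to be categorized, after attempts and preparatory behavior.

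**The concern.** The first sentence of the counting rule leads a reader to expect, for each category, the number of patients who had that event. The second sentence changes this for every category that is not the patient's maximum. Self-injury is the extreme case because every other category outranks it. Its row therefore counts only patients who report self-injury and nothing else in the interval, but nothing in the row label says so.

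The ranking also lacks support in the protocol. A most-severe rule makes sense along one severity scale. Protocol 12.1.18 gives no ground for treating self-injury as a milder form of ideation.

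At stake is a by-arm count within a named safety variable: SAP 6 lists the incidence of suicide-related events on the C-SSRS among its safety variables. Someone comparing arms on self-injury would be reading a residual category without knowing it.

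**Working it through.** **Inputs.** The category list, its order and the counting rule come from SAP 6.6. The description of the scale is in Protocol 12.1.18, and the post-treatment visits (weeks 2, 4, 6, 8 and 12) are in Protocol 8.3.4 and 8.3.5. The comparison table is in SAP 6.2.

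**1. Reproduce the SAP's count.** 1 self-injury + 5 ideation + 5 behavior = 11, as stated.

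**2. Rank.** The order is increasing, so the first-listed category has rank 1 and the last has rank 11. Self-injury has rank 1.

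**3. Apply the rule.** Within an interval, the category kept is the one with the maximum rank. Pair self-injury with each other category k = 2, …, 11: max(1, k) = k every time. Self-injury is kept in 0 of 10 pairings. It is the only category outranked by all the others.

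**4. Effect of the undefined interval.** Two example patients:

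| Responses | Interval = visit window | Interval = whole treatment period |
|---|---|---|
| Self-injury and wish to be dead, both at week 2 | wish to be dead only | wish to be dead only |
| Self-injury at week 2, wish to be dead at week 4 | both rows | wish to be dead only |

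The first patient is missing from the self-injury row on either reading. The second is missing only on the broader one. The reading changes the extent of the omission but does not remove it.

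**5. Size in patients.** If n patients report self-injury and a fraction q of them report another item in the same interval, the row shows n(1 − q). The documents give neither n nor q, so no patient number follows.

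**6. Comparison with SAP 6.2.** The adverse event table works per row: "The number and percentage of patients reporting each event will be summarized and presented for all events and tabulated by treatment groups", and at each level "a patient will be counted once if he/she reports 1 or more experiences at that level". A patient with two different preferred terms appears under both. In SAP 6.6, a patient with two different kinds of event in one interval appears under one.

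**7. Protocol placement.** Protocol 12.1.18 puts self-injury in two places: as a third item beside ideation and behavior, and within the list of behaviors. Under that section, a positive answer to any item in the behavior section must be reported as a serious adverse event, whereas ideation questions 1 to 3 are left to the investigator's judgment. On neither placement does self-injury fall below ideation.

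**8. After the change.** With self-injury on its own line and out of the ranking, a patient with self-injury is counted there in 10 of 10 pairings, on either reading of the interval.

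**The case against.** **Most-severe counting is a convention, and it is disclosed.** SAP 6.2 uses it too, taking the worst severity grade in its second tabulation. That is correct, but there it operates within a given adverse event of a patient. In SAP 6.6 it operates across different kinds of event.

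**The interval is clear enough from the preceding sentence, and there is only one treatment cycle.** That is a fair reading and perhaps the natural one. It settles the ambiguity but makes the omission as wide as it can be.

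**Other outputs cover the gap.** This stands in large part. The patient stays in the table under another category, and SAP 2.3 provides for listing the data. Self-injury recorded as an adverse event reaches the by-arm tables of SAP 6.2, or of SAP 6.3 if serious. If self-injury belongs to the behavior section, as one sentence of Protocol 12.1.18 suggests, serious reporting is mandatory. What remains is narrow: a listing is not a by-arm incidence, and a patient could count under self-injury in the adverse event table yet be absent from the C-SSRS self-injury row.

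**A reader might infer a larger fault: that the whole ladder is wrong, because any behavior item also displaces ideation, and that most of its C(11,2) = 55 category pairs cross constructs.** The documents do not support a figure for this. With self-injury as a third construct, the crossing pairs number 5 + 5 + 25 = 35, leaving 20 within constructs. With self-injury among the behaviors, they number 5 × 6 = 30, leaving 10 + 15 = 25. Protocol 12.1.18 supports both groupings, and pairs of categories are not patients.

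**Nor is the matching larger remedy free.** Suppose ideation and behavior were each counted once, at their worst, from injection to exit. If the interval is a visit window, a patient with a wish to be dead at week 2 and active ideation with intent at week 8 now appears in both rows. That remedy would drop the first.

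**Conclusion.** The point holds for the self-injury row. As written, SAP 6.6 counts only patients whose self-injury is unaccompanied by any other C-SSRS item in the interval, and the protocol offers no basis for ranking self-injury below ideation. This follows from the list order and the word *increasing*. It needs no assumption about incidence or about the meaning of the interval.

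The size is modest. One row of one descriptive table is affected. The number of patients with any suicide-related event, the listings and the adverse event and serious adverse event tables do not change, and no efficacy, power or type I error figure is involved. It would be wrong to infer that patients with self-injury drop out of the safety reporting, or that the ranking of behavior over ideation has been shown to be a fault. This is a free improvement.

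**What to change.** Keep the existing most-severe rule for the ideation and behavior categories, and add one sentence to SAP 6.6:

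> Self-injurious behavior without suicidal intent will be reported on its own line as the number and percentage of patients with at least one such response from injection to exit, regardless of other items reported, and will not enter the most-severe ranking.

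The row already exists and the responses are already collected, so no new data and no protocol change are needed. The new line has a stated period and does not depend on how the interval is read for the other ten categories. Because a patient may now appear on the self-injury line and on another line, a table footnote should say that the lines are not to be added together.

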6.7 Other Safety Analyses

6.7.1 Physical Examination

Physical examination will be performed at screening and study exit. Abnormal findings will be listed.

6.7.2 Pregnancy Test

The urine pregnancy test will be performed for females of childbearing potential at screening, day 1 prior to injection and at study exit. Positive pregnancy test results (any pregnancies will be reported in the clinical study report) will be listed.

7 Interim Analyses

No interim analysis is planned for this study.

8 Pharmacokinetic Data Analyses

There will be no pharmacokinetic data to be analyzed from this study.

9 Health Outcomes Data Analyses

There will be no health outcomes data to be analyzed from this study.

10 Analysis for US FDA HFD-550

Analyses are as described in all preceding sections except for the items described below.

10.1 Primary Efficacy Analyses

There are 2 co-primary endpoints: the average grade change from baseline in the MAS-B of the principal muscle group at weeks 4 and 6 and the average CGI by Physician at weeks 4 and 6. For both co-primary endpoints, the statistical null hypothesis is that both the higher dose (6 U/kg) and the lower dose (3 U/kg) have the same mean as placebo. The alternative hypothesis is that at least one study dose has a different mean than placebo. In addition to the primary statistical analyses cited in Section 5.2.1 for the average grade change from baseline in MAS-B score of the principal muscle group at weeks 4 and 6, the average CGI by Physician at weeks 4 and 6 will be analyzed using the same statistical method with a same MMRM model in Section 5.3.1.

The Hochberg procedure ([Hochberg and Tamhane, 1987](#)) will be used to control the family-wise type I error rate. With 2 doses and 2 co-primary endpoints in each dose, the maximum p-value for the 2 co-primary endpoints in each dose will be used in the Hochberg procedure. We first define the following values:

p11: p value for Botox 6 U/kg vs placebo comparing MAS-B

p12: p value for Botox 3 U/kg vs placebo comparing MAS-B

p21: p value for Botox 6 U/kg vs placebo comparing CGI

p22: p value for Botox 3 U/kg vs placebo comparing CGI

$p1 = \max(p11, p21)$, $p2 = \max(p12, p22)$.

$p1$ and $p2$ will be sorted in an increasing order to get $p(1) \leq p(2)$. The following decision rule will then be applied:

Step 1: If $p(2) \leq 0.05$, both doses are considered efficacious; otherwise go to step 2.

Step 2: If $p(1) \leq 0.025$, its corresponding dose is considered efficacious; otherwise go to step 3.

Step 3: Neither dose is considered efficacious.

For sensitivity analysis purposes to supplement the co-primary analyses, ANCOVA using MI for missing values will be conducted for the co-primary endpoints of MAS-B and CGI. The model will include baseline MAS-B as a covariate and factors of age group, principal muscle group, treatment group, study center, and previous botulinum toxin exposure. A summary of the percentages of missing MAS-B and CGI scores by visit will also be provided. Additional sensitivity analyses for the MAS-B changes from baseline and CGI scores at each assessment timepoint will also be performed using the same ANCOVA with observed data, and linear contrasts will be used to estimate the treatment differences between each study dose and placebo.

